Title: Evaluating the Safety, Tolerability, Pharmacokinetics and Receptor Occupancy of BMS-984923

ClinicalTrials.gov ID: NCT04805983

Date: 12/15/2021

Document: Protocol and SAP

**HRP-503B – BIOMEDICAL RESEARCH PROTOCOL
(2016-1)**

Protocol Title: An Open-Label, Single-Ascending Dose Study to Evaluate the Safety, Tolerability, Pharmacokinetics and Receptor Occupancy of BMS-984923

Principal Investigator: [name], PhD

Version Date: November 29, 2021

(If applicable) Clinicaltrials.gov Registration #: NCT04805983

INSTRUCTIONS

This template is intended to help investigators prepare a protocol that includes all of the necessary information needed by the IRB to determine whether a study meets approval criteria. **Read the following instructions before proceeding:**

1. Use this protocol template for a PI initiated study that includes direct interactions with research subjects. Additional templates for other types of research protocols are available in the system Library.
2. If a section or question does not apply to your research study, type “Not Applicable” underneath.
3. Once completed, upload your protocol in the “Basic Information” screen in IRES IRB system.

SECTION I: RESEARCH PLAN

1. **Statement of Purpose:** State the scientific aim(s) of the study, or the hypotheses to be tested.

Primary Objective: To evaluate the safety, tolerability, and pharmacokinetics of BMS-984923 in healthy participants.

Secondary Objective: A receptor occupancy substudy will determine drug receptor occupancy at each dose using [¹⁸F]FPEB PET.

2. **Probable Duration of Project:** State the expected duration of the project, including all follow-up and data analysis activities.

Each participant will complete a screening period of up to 90 days, a treatment period of up to two days and a follow up period of seven days. The total duration of participation in this study is approximately 14 weeks.

The study will enroll up to six cohorts of 6 participants each. Study drug will be administered in sequentially increasing dose groups. For all 6 participants at a dose cohort, a safety assessment review will be completed prior to advancing the next higher dose level.

It is anticipated that enrollment will occur in less than 15 months and all protocol activities will be completed in less than 18 months, with up to 12 months for data analysis.

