1994) will be administered prior to oral dose administration, again at approximately 6 hours post-dose (approximate peak concentration) and approximately 24 hours post-dose.

If a participant is found to be depressed, a clinician will perform further assessment and refer the participant to care as necessary. As part of ongoing adverse event monitoring, participants will be asked about changes in mood during in-person and phone visits. Additionally, they will be advised to call to inform the study team of changes in mood, specifically depression, between visits.

Blood will be collected for safety laboratory studies prior to drug dose administration and on Days 2 and 3. Safety laboratory studies will include a comprehensive metabolic panel [glucose, blood urea nitrogen (BUN), creatinine, sodium, potassium, chloride, bicarbonate, calcium, total protein, albumin, total bilirubin, alkaline phosphatase, aspartate transaminase (AST), alanine transaminase (ALT)], phosphate, a lipid panel [total cholesterol, low density lipoprotein (LDL), high density lipoprotein (HDL), triglycerides], a complete blood count and differential, lactate acid dehydrogenase (LDH), creatine kinase (CK), amylase, and a urinalysis with reflex microscopic examination.

Plasma will be collected for PK analysis as shown in [Table 4](#).

A 24-hour urine collection will be performed starting at the time of study drug administration. A second 24-hour urine collection will be performed from 24-48 hours after study drug administration. These samples will be used to measure urine drug and metabolite levels.

The participant will remain in the HRU on Study Days 1 and 2, and discharged on Study Day 3 after all required assessments have been completed. During the inpatient stay, abnormal assessments and laboratory values will be evaluated by the PI in collaboration with the medical monitor in real time. See the schedule of events ([Table 3](#)) for details on the assessments on each Study Day.

Post Treatment Follow-up Visits

See the schedule of events ([Table 3](#)) for details on the assessments on each Study Day.

Visit 3 (Day 4) – Vital signs (BP, pulse, respiratory rate, and oral body temperature) will be obtained. Plasma samples for PK assessments will be collected. Information on changes or newly administered concomitant medications as well as any new or ongoing (S)AEs will be collected at each visit.

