Dose escalation decisions will be determined with the following approach. At the completion of each cohort, 0-72 h PK data will be used to assess the plasma exposure derived from the area under the curve (AUC) from 0-24 h. Our dose escalation decisions will be based on the human data relative to the rat 28 day GLP toxicology study to determine maximal NOAEL. In that study, the plasma exposure at NOAEL based on AUC (0-24h) was 192,000 ng*h/mL (see IB). Furthermore, the plasma exposure in corresponding Cynomolgus study was similar at 169,000 ng*h/mL.

The maximal doses for each cohort will be 10, 40, 70, 100, 150 and 200 mg. The human equivalent dose derived from the NOAEL dose in the 28D toxicology study in the most sensitive species (rat) is 140 mg. Thus, the starting dose is less than 10% of the 140 mg amount. Dose escalation in cohorts 2-6 will follow the plan above, but will be decreased based on the observed plasma exposure of the AUC (0-24 h) as detailed in the schedule below. The dose escalation for the next cohort will be based on the most recent cohort observed PK analysis as follows:

If plasma $AUC_{0-24h} < 24,000 \text{ ng}^*\text{h}/\text{ml}$ (12.5% NOAEL), then dose increase according to schedule
 If plasma $AUC_{0-24h} 24,000-48,000 \text{ ng}^*\text{h}/(12.5-25\% \text{ NOAEL})$, then dose increase maximum of 2 fold
 If plasma $AUC_{0-24h} 48,001-96,000 \text{ ng}^*\text{h}/\text{ml}$ (25-50% NOAEL), then dose increase maximum of 1.5 fold
 If plasma $AUC_{0-24h} 96,001-120,000 \text{ ng}^*\text{h}/\text{ml}$ (50-67.5% NOAEL), then dose increase maximum of 1.3 fold
 If plasma $AUC_{0-24h} > 120,000 \text{ ng}^*\text{h}/\text{ml}$ (>67.5% NOAEL), then stop escalation

Any serious adverse events or other safety concern might also constitute a rationale to stop or reduce escalation.

Criteria for intervention discontinuation

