The DSMB will review all non-serious AEs at the completion of each dose cohort (approximately every 3 months). This will be done via teleconference.

The IND holder ([name]) will report adverse events to the FDA following Guideline Section 312.32 IND Safety Reporting standards. In particular, the sponsor will notify FDA in an IND safety report of potential serious risks, from clinical trials or any other source, as soon as possible, but in no case later than 15 calendar days after the sponsor determines that the information qualifies for reporting. Upon request from FDA, the IND holder will submit to FDA any additional data or information that the agency deems necessary, as soon as possible, but in no case later than 15 calendar days after receiving the request. The IND holder will also notify FDA of any unexpected fatal or life-threatening suspected adverse reaction as soon as possible but in no case later than 7 calendar days after the sponsor's initial receipt of the information.

13. Statistical Considerations: Describe the statistical analyses that support the study design.

Sample Size

The sample size was derived empirically from experience with previous single ascending dose clinical studies and PET occupancy studies in other disorders and is deemed appropriate to achieve the study objectives.

General Methods

Data will be tabulated by dose cohort, as well as by pooled (all participants combined), and no inferential statistics are planned.

Handling of Missing Data

All data collected will be included in by-domain data listings, sorted by participant number and time point, or as appropriate. Every attempt will be made to collect data at each time point. For participants who discontinue treatment (for any reason), participants will continue to be followed and efficacy endpoints and safety data collected where possible.

Subgroups

The sample size precludes analysis by-subgroup. However, exploratory assessment of any trends among subgroups (eg, by dose) may be performed, after initial review if the data warrant.

Analysis Populations

Safety Population: Safety outcomes will be assessed for all participants who are given at least one dose of study drug.

Alpha Level Considerations

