- Clinical laboratory tests presented as changes over time. Potentially clinically significant (PCS) ranges will be defined and used to determine the incidence of participants experiencing new-onset PCS laboratory values, where new-onset is defined as a PCS value for a participant following initiation of study treatment for which the participant did NOT have a PCS value for that analyte PRIOR to initiation of study treatment.
- Vital signs including: respiratory rate, heart rate, temperature, and blood pressure, as per the schedule of events. BMI will be assessed, with height collected only at screening.
- Physical examination
- 12-lead ECG. ECG parameters will be analyzed in a fashion similar to that of clinical laboratory parameters.

Concomitant treatments will be assessed according to the timing of their start/stop dates as they relate to the study drug treatment, as follows:

- Prior medications with start AND stop date before date of first dose of study drug.
- Concomitant medications with participant exposure that includes at least one dose of study drug.
- New-onset medications. Concomitant medications with a start date AFTER the first dose of study drug. New-onset medications are a subset of the full set of concomitant medications.

Changes from pre-treatment will be calculated in a similar fashion as for the efficacy endpoints, but no inferential statistics will be provided for safety endpoints. Shifts from baseline in ECG will be tabulated for heart rate and QTc. Other endpoints will be assessed according to the scale of the variable.

Pharmacokinetic Endpoints

Concentration data in plasma will be assessed descriptively over time. Correlation with safety and receptor occupancy outcomes may be performed, as the data warrant.

SECTION II: RESEARCH INVOLVING DRUGS, BIOLOGICS, RADIOTRACERS, PLACEBOS AND DEVICES

If this section (or one of its parts, A or B) is not applicable, check off N/A and delete the rest of the section.

A. RADIOTRACERS

N/A

1. Name of the radiotracer: $[^{18}\text{F}]$ FPEB
2. Is the radiotracer FDA approved? YES NO

If NO, an FDA issued IND is required for the investigational use unless RDRC assumes oversight.

3. Check one: IND# 150912

or RDRC oversight (RDRC approval will be required prior to use)

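### Pharmacokinetics is a primary objective, but Section 13 plans only descriptive plasma concentrations, and nowhere is the human dose-exposure relation over 10-200 mg estimated

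*Combined protocol and SAP*

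**What the plan says.** - **Objective.** Section I, item 1 (Statement of Purpose) gives the primary objective: "To evaluate the safety, tolerability, and pharmacokinetics of BMS-984923 in healthy participants".
- **Planned PK analysis.** Section 13, Pharmacokinetic Endpoints, has two sentences. The first is "Concentration data in plasma will be assessed descriptively over time". The second is optional: "Correlation with safety and receptor occupancy outcomes may be performed, as the data warrant". No PK parameter, PK population, summary statistic or dose-exposure estimate is named.
- **General approach.** Section 13, General Methods, tabulates data by cohort and pooled, and states that "no inferential statistics are planned". Under Subgroups, a look at trends by dose is allowed but optional, and it is not specific to PK.
- **Doses.** Section 12, Safety Assessment and Dose Escalation Decisions: "The maximal doses for each cohort will be 10, 40, 70, 100, 150 and 200 mg".
- **AUC.** The same section says that after each cohort "0-72 h PK data will be used to assess the plasma exposure derived from the area under the curve (AUC) from 0-24 h". It then sets caps on the size of the next dose step: "The dose escalation for the next cohort will be based on the most recent cohort observed PK analysis as follows". It does not say whether the cohort AUC is a mean, a median or a maximum.
- **Urine.** Two 24-hour collections are planned (Section 4, In-patient Treatment, Visit 2): "These samples will be used to measure urine drug and metabolite levels". Section 13 does not mention urine.
- **Linearity.** The only remark on linearity with dose is in the Background and concerns mice.

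**The concern.** How exposure changes with dose is a central PK question in an ascending-dose study. Here it belongs to the primary objective, and the samples to answer it are already scheduled out to Day 7. Tables of concentrations by cohort and time do not answer it. With six people per cohort, each cohort's typical exposure is known only roughly, and comparing adjacent doses says little about proportionality.

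Two things are at stake. The report of a first-in-human study could end without a quantified dose-exposure relation to carry into later studies. And because the study is open-label, with neither the parameters nor the model fixed in advance, both could be chosen after the data have been seen.

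**Working it through.** **The plan's own figures.** Six cohorts of six give 36, as stated in Section 4. The dose range is 200/10 = 20-fold. The sample size is described as empirical, with no effect size, CV, power or precision, so there is no PK precision figure to reproduce.

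**Assumption.** The between-participant CV of AUC is not in the documents. I use 30% and 50%. On the log scale σ = √ln(1 + CV²), which gives 0.294 and 0.472.

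**1. One cohort alone (n = 6).** The 95% factor for a geometric mean is exp(t₅ × σ/√6), with t₅ = 2.571.
- CV 30%: exp(2.571 × 0.1198) = 1.36
- CV 50%: exp(2.571 × 0.1928) = 1.64

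**2. Two adjacent cohorts (n = 6 each).** The 90% half-width for a log-log slope is t₁₀ × σ × √(2/6) / ln(dose ratio), with t₁₀ = 1.812.
- 40 to 70 mg: ±0.55 (CV 30%) to ±0.88 (CV 50%)
- 150 to 200 mg: ±1.07 to ±1.72

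These are too wide to be useful.

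**3. Pooled slope.** The model is ln(AUC) = a + b × ln(dose), with SE(b) = σ/√Sxx.

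| Data | Sxx | df | CV | SE(b) | 90% half-width |
|---|---|---|---|---|---|
| 36, 10-200 mg | 35.35 | 34 | 30% | 0.0494 | 1.691 × 0.0494 = 0.083 |
| 36, 10-200 mg | 35.35 | 34 | 50% | 0.0795 | 1.691 × 0.0795 = 0.134 |
| 24, 10-100 mg | 18.44 | 22 | 30% | 0.0684 | 1.717 × 0.0684 = 0.117 |
| 24, 10-100 mg | 18.44 | 22 | 50% | 0.1100 | 1.717 × 0.1100 = 0.189 |

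The 24-participant rows are included because Section III, item 1 gives four cohorts of six. I assume these would be the four lowest doses.

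Over 20-fold in dose, ±0.083 to ±0.134 corresponds to a factor of 20^0.083 = 1.28 to 20^0.134 = 1.50 either way. For scale, AUC would rise 20^0.8 = 11-fold, 20-fold or 20^1.2 = 36-fold for slopes of 0.8, 1.0 and 1.2.

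**4. What drives the slope.** Mean ln(dose) is 4.192 and ln(10) is 2.303. The 10 mg cohort contributes 6 × (2.303 − 4.192)² = 21.4 of 35.35, or 61%. The slope is therefore a global average dominated by 10 mg against the rest, and bending among the higher doses could be missed.

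**5. Do the caps need proportionality over 20-fold?** Take the top of each AUC band in Section 12 and apply the largest permitted step. The lowest band follows the schedule, whose largest step is 40/10 = 4-fold. The critical slope is ln(192,000/AUC)/ln(fold), where 192,000 ng·h/mL is the rat reference exposure.

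| Band top | Step | Next AUC if proportional | Slope at which the step reaches 192,000 |
|---|---|---|---|
| 24,000 | 4 | 96,000 | 1.50 |
| 48,000 | 2 | 96,000 | 2.00 |
| 96,000 | 1.5 | 144,000 | 1.71 |
| 120,000 | 1.3 | 156,000 | 1.79 |

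Against the monkey figure of 169,000 the critical slopes are 1.41, 1.82, 1.40 and 1.31. Each cap assumes something about the slope for one step only, and the next observed AUC resets it.

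**The case against.** The strongest reply is that the trial is openly descriptive and already derives AUC from 0 to 24 h for every cohort, and that Section 13 permits exploratory looks by dose. On this view a power model is a matter of preference. Part of this stands. The document as a whole does more than describe concentrations, and omitting a list of standard PK parameters would, by itself, be only missing detail. The rest does not stand. The AUC sits in the escalation rules with no defined summary and no place in the analysis section, and an optional look at trends is not a plan for a primary objective. A slope with an interval is estimation, so it does not conflict with planning no inferential tests.

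It is also fair to object that one log-linear slope assumes constant curvature-free behaviour and leans heavily on the 10 mg cohort. That stands, and it is why a curvature check belongs in the fix.

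A reader might infer two stronger points that the documents do not support.

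- **That the escalation caps rely on proportionality over the whole range.** They use the most recent cohort's observed AUC, the permitted step shrinks as AUC rises, and escalation stops above 120,000 ng·h/mL.
- **That the rat toxicity attributed to accumulation makes non-proportionality the main PK risk here.** Section 10 links that toxicity to repeated dosing, with onset over days. Each participant in this study receives a single dose, and accumulation is a different matter from single-dose non-proportionality.

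**Conclusion.** The point holds as a gap in the analysis plan for a primary objective. Section 13 commits only to describing concentrations, and no section estimates the human dose-exposure relation. It is not a finding about the safety of the escalation rules.

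The gap is worth closing because the planned data are informative when pooled. The expected 90% half-width for the slope is about 0.08-0.13 with 36 participants. It is about 0.12-0.19 with 24, if those are the 10-100 mg cohorts. Adjacent-cohort comparisons give ±0.55 at best. These figures rest on an assumed CV of 30-50%, on six evaluable participants per dose, and on exposure being roughly log-linear in dose.

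**What to change.** Replace the PK text in Section 13 with the following elements:

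1. **Parameters per participant:** AUC0-24h (the metric Section 12 already uses), AUC0-last, AUC0-inf where estimable, Cmax, Tmax, half-life and CL/F, plus the amount excreted in urine over 0-24 h and 24-48 h. Report geometric mean and CV by dose, and define the PK population.
2. **Dose-exposure estimate at end of study:** fit ln(parameter) = a + b × ln(dose) over all dosed participants for AUC and Cmax. Report b with its 90% confidence interval as an estimate, not a test.
3. **Check of the model:** plot dose-normalised exposure by cohort to look for curvature, because the 10 mg cohort carries about 61% of the information on the slope.

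Separately, reconcile the enrolment figures: about 36 in six cohorts (Section 4) against 24 in four cohorts (Section III, item 1). The 20-fold range exists only under the six-cohort version.

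The cost is a paragraph of SAP text, a simple regression and one checkable assumption of log-linearity. It needs no extra samples, visits or participants, and no dose or escalation rule changes.
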